#### 8. Withdrawal criteria

Subjects will be withdrawn from the study if the following criteria are met:

- (1) If the subject expresses a desire to withdraw from the study.
- (2) If it is discovered that the subject is clearly ineligible for study participation.
- (3) If investigators/subinvestigators determine that AEs make continued participation in the study difficult.
- (4) If investigators/subinvestigators determine that continuation of the study is inappropriate for a subject, such as if hyperviscosity syndrome occurs or if control of Hb within the target range is impossible.
- (5) If continuous haemodialysis is initiated, or if the subject receives a renal transplant.
- (6) If renal function recovers such that peritoneal dialysis is discontinued.
- (7) If pregnancy of the subject is discovered.
- (8) If the investigator/subinvestigator determines a subject should withdraw from the study for any other reason.

#### 9. Target sample size

Forty subjects enrolled in treatment period.

##### 9.1 Rationale for target sample size

Assuming a SD of 1.78 for mean Hb, which is one of the efficacy endpoints for the study, a sample size of 40 subjects allows for value estimation with a precision of  $\text{mean} \pm 0.57$  g/dL (95% CI). The SD of 1.78 was calculated from the upper limit of the 80% CI in the MT-6548 300 mg group at the end of the primary efficacy evaluation period of 6 weeks in study CI-0021, a dose-finding study in Japanese patients with NDD-CKD-related anaemia. According to JSDT's "Guideline for Renal Anemia in Chronic Kidney Disease 2015," Hb values vary in a range of about 1 g/dL in normal clinical contexts, so a level of precision of  $\text{mean Hb} \pm 0.57$  g/dL (95% CI) should allow for a clinically meaningful analysis. A sample size of 40 subjects should also enable analysis of safety.

#### 10. Study period

## 11. Test and observation schedule

Item	VISIT	Informed consent	Screening period [a]		Treatment period										Final day of follow-up observation period [b]
			First day	Visit 2	First day [c]	W2	W4	W6	W8	W10	W12	W16	W20	W24	
Visit no.	IC	SV1	SV2	TV1	TV2	TV3	TV4	TV5	TV6	TV7	TV8	TV9	TV10	TV11	FU
Permitted range (day)	-	-	-	-	±3	±3	±3	±3	±3	±3	±7	±7	±7	+ 7 or + 14 [d]	+7
Procedure/evaluation															
Informed consent	X														
Inclusion/exclusion criteria	X	X	X	X											
Patient's background and history	X			X											
Height				X											
Body weight (weight excluding dialysis solution)				X					X				X	X	
Folic acid and vitamin B 12		X													
Pregnancy test [e]		X											X	X	
Haematology test		X	X [f]	X	X	X	X	X	X	X	X	X	X	X	X
Blood biochemistry test		X		X	X	X	X	X	X	X	X	X	X	X	X
C-reactive protein		X		X									X	X	
Iron-related measures		X		X	X	X	X	X	X	X	X	X	X	X	X
Hepcidin				X	X	X	X		X				X	X	
Erythropoietin				X	X	X	X		X				X	X	
VEGF				X					X				X	X	
Urinalysis (qualitative)		X		X	X	X	X	X	X	X	X	X	X	X	X
Vital signs [g]		X		X	X	X	X	X	X	X	X	X	X	X	X
12-lead ECG [h]				X									X	X	
Fundoscopy [d]			X										X	X	
Chest X-ray [d]			X										X	X	
QOL measures (EQ-5D-5L, KDQOL)				X						X			X	X	
AE investigations				X	X	X	X	X	X	X	X	X	X	X	X
Blood sampling for genetic analysis [i]					Blood sampling should be performed once as early as possible after 2 weeks of										
Drug evaluation/procedure															
Investigation of concomitant drugs				X	X	X	X	X	X	X	X	X	X	X	X
Prescribing MT-6548 tablets [j]				Administration according to the dosage adjustment guideline											
Administration of iron supplements				Administer iron supplements to maintain serum ferritin values ≥100 ng/mL or TSAT ≥20%.											

[a] Maximum screening period length is 6 weeks. Test results will be reviewed prior to transitioning from the first day of the screening period to screening period Visit 2, and from screening period Visit 2 to the first day of the treatment period. Re-testing will be performed as necessary.

[b] Not required if withdrawing prior to treatment period.

[c] Perform prior to study drug treatment (AE investigations begin after study drug treatment)

[d] Fundoscopy and chest X-ray performed once during screening period and during Weeks 20 and 24 of treatment period. Also performed to extent possible within 14 days of study withdrawal.

[e] Only female subjects who may become pregnant.

[f] Hb only measured.

[g] Measured to extent possible prior to blood sampling. Measured with subject sitting after 5 minutes of rest.

[h] Measured to extent possible prior to blood sampling. Measured with subject in supine position after 5 minutes of rest.

[i] Blood sampling for genetic analysis performed once as early as possible after Week 2 of treatment period in subjects who have granted consent.

[j] Prescribe MT-6548 Tablet depending on quantity of subject's remaining study drug. Subjects are

instructed to open new bottles of study drug only after completing previous bottle.

## 1. Protocol history and background information

### (1) Target disease and treatment methods

Chronic kidney disease (CKD) is defined in Japanese Society of Nephrology's "Clinical Practice Guidebook for Diagnosis and Treatment of Chronic Kidney Disease 2012" as renal disorders (e.g., proteinuria) or renal impairment with glomerular filtration rate (GFR) of  $<60 \text{ mL/min/1.73m}^2$  for 3 or more months.

CKD is a significant public health problem throughout the world, and in Japan alone 20% of adults are estimated to have GFR of  $<60 \text{ mL/min/1.73m}^2$ . In Japan there are more than 300,000 CKD patients requiring dialysis, a number which has increased in the past 30 years.

Anaemia is a well-known complication of renal disease, and occurs early after onset of CKD. Prevalence of anaemia increases as CKD progresses, with 53% to 89% of dialysis patients affected by the disease. Causes of anaemia in CKD patients include exsanguination, reduced RBC (red blood cell) lifespan, iron deficiency, erythropoietin (EPO) deficiency, [REDACTED]. The primary cause of nephrogenic anaemia is EPO deficiency, which results from hypoxic disorders or cells surrounding renal tubules or cell decrease in cells surrounding renal tubules. [REDACTED]

Further, iron loss due to dialysis is an extremely important cause of anaemia in CKD and requires iron supplementation. Anaemia significantly affects organ function by decreasing oxygen transport to tissue, resulting in various symptoms such as fatigue, shortness of breath, and exercise intolerance. Compensatory changes occur in the structure and function of the heart in these anaemia patients, including increased cardiac output and left ventricular hypertrophy, which can ultimately result in cardiac failure. Other anaemia-related disorders observed in CKD patients include cognitive function disorders, sleep disorders, and impaired immune function, sometimes resulting in reduced quality of life (QOL). Anaemia is also a factor related to poor prognosis in CKD patients. Improving anaemia results particularly in markedly improved QOL in terms of energy, fatigue, and physical function.

Peritoneal dialysis involves injecting dialysis solution into the peritoneal cavity and allowing it to remain for a period of time so that the peritoneum may purify the blood. As of the end of 2015, 2.9% of all dialysis patients in Japan were using this method (according to the JSDT's "Summary of Chronic Dialysis Treatment in Japan 2015".) Peritoneal dialysis is fundamentally positioned as initial comprehensive renal replacement therapy for Stage 5 CKD patients. Beginning the treatment in a planned manner while the patient still maintains renal function is considered crucial for avoiding complications during introduction and improving prognosis (2009 JSDT "Guideline for Peritoneal Dialysis"). Further, the clinical status of patients with peritoneal dialysis-related chronic kidney disease (PD-CKD) is extremely similar to that of

[REDACTED]

[REDACTED]

[REDACTED]

[REDACTED]

[REDACTED]

[REDACTED]

[REDACTED]

[REDACTED]

[REDACTED]

[REDACTED]

[REDACTED]

[REDACTED]

[REDACTED]

[REDACTED]

[REDACTED]

[REDACTED]

[REDACTED]

[REDACTED]

[REDACTED]

[REDACTED]

[REDACTED]

[REDACTED]

[REDACTED]

[REDACTED]

[REDACTED]

[REDACTED]

[REDACTED]

(4) Investigational plan

The current study will evaluate efficacy and safety of MT-6548 in patients with PD-CKD-related anaemia.

Based on results of clinical studies to date, the treatment period is set at 24 weeks, an appropriate period to enable evaluation of MT-6548 efficacy in terms of Hb improvement maintenance and switching maintenance.

MT-6548 dosage is set based on results to date at an initial dosage of 300 mg, with maintenance dosages of 150–600 mg.

## 2. Study objectives.

The purpose of the study is to evaluate efficacy and safety of MT-6548 in patients with PD-CKD-related anaemia.

### 3. Subjects

#### 3.1 Subjects

Patients with PD-CKD-related anaemia

#### 3.2 Inclusion criteria

Subjects must meet all inclusion criteria below and have capacity to grant informed consent. Laboratory tests to determine inclusion criteria will be performed at a central testing facility. If a given laboratory test is performed multiple times during the screening period, the most recent test will be used for determination.

- (1) Patients at least 20 years of age as of the day of consent (either sex)
- (2) Patients with CKD diagnosed according to the Japanese Society of Nephrology's "Clinical Practice Guidebook for Diagnosis and Treatment of Chronic Kidney Disease 2012" as of the day of consent.
- (3) Patients who have been receiving peritoneal dialysis for at least 4 weeks prior to the first day of the screening period, but excluding patients also receiving haemodialysis.
- (4) Patients expected to initiate haemodialysis during the treatment period.
- (5) Correction cohort: Patients who have not received ESA treatment 8 weeks prior to the first day of the screening period. However, patients receiving ESA treatment at consent may join the study if they discontinue this treatment after consent and have a washout period of at least 8 weeks.

Conversion cohort: Patients receiving the same formulation of ESA using the same administration route and the same dose interval (the dose interval should be the one described in the package insert for the ESA formulation) within 8 weeks prior to the first day of the screening period, using the dosages described below.

Dosage:

- ✓ Epoetin alfa (recombinant) and epoetin beta (recombinant):  $\leq 12,000$  IU every 2 weeks
  - ✓ Darbepoetin alfa (recombinant):  $\leq 120$   $\mu$ g every 2 weeks
  - ✓ Epoetin beta pegol (recombinant):  $\leq 250$   $\mu$ g every 4 weeks
- (6) Patients with the following mean Hb values during screening, using the mean of the latest two tests:
    - ✓ Correction group:  $\geq 8.0$  g/dL,  $< 11.0$  g/dL
    - ✓ Conversion group:  $\geq 9.0$  g/dL,  $< 12.5$  g/dL
  - (7) Patients with a difference of  $< 1.5$  g/dL in Hb for the latest two tests in the screening period
  - (8) Patients with serum ferritin values of  $\geq 100$  ng/mL or transferrin saturation (TSAT) of  $\geq 20\%$  during the screening period.

- (9) Patients with folic acid and vitamin B12 values above standard minimum values during the screening period.

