#### Rationale

- (1) Individuals are legally capable of granting consent as of 20 years of age. There is no particular basis for limiting participation to either sex.
- (2) To ensure that subjects have the target disease of CKD.
- (3) (4) Set because target patients are those receiving peritoneal dialysis with no concomitant haemodialysis
- (5) The 8-week timespan was set in consideration of ESA's half-life and RBC life-span. ESA type, route of administration, and dose interval were restricted in order to control Hb value fluctuations. ESA dosage may be adjusted to maintain Hb levels as required, but only patients whose dosage does not exceed the normal maintenance dosage described in the package insert are eligible for the study.
- (6) Set with reference to target Hb values in nephrogenic anaemia therapy according to JSDT's "Guideline for Renal Anemia in Chronic Kidney Disease 2015."
- (7) Set to ensure appropriate efficacy evaluation by targeting patients without significant fluctuations in Hb levels.
- (8) Set to ensure patients without iron insufficiency, using as reference criteria for initiating iron supplementation therapy according to the JSDT's "Guideline for Renal Anemia in Chronic Kidney Disease 2015."
- (9) Set to ensure appropriate efficacy evaluation by targeting patients without insufficiencies in folic acid or vitamin B12, required for hematopoiesis.

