### 3.3 Exclusion criteria

Patients who meet any of the following exclusion criteria will be excluded. Laboratory tests to determine exclusion criteria will be performed at a central testing facility. If blood pressure measurements or a given laboratory test is performed multiple times during the screening period, the most recent test will be used for determination.

- (1) Patients with anaemia resulting primarily from a disease other than CKD after date of consent (e.g., sickle-cell syndrome, myelodysplastic syndrome, myelofibrosis, haematopoietic malignancy, myeloma, haemolytic anaemia, thalassemia, or aplasia pure red cell)
- (2) Patients with active haemorrhaging or exsanguination within 8 weeks prior to the first day of the screening period.

- (3) Patients who have received RBC transfusion within 8 weeks prior to the first day of the screening period.
- (4) Patients who have received testosterone enanthate or mepitiostane within 8 weeks prior to the first day of the screening period.
- (5) Patients determined by investigators/subinvestigators to likely require immediate rescue therapy or drug holiday of the study drug after initiation of treatment period.
- (6) Patients expected to no longer require peritoneal dialysis during the study period due to recovery of renal function.
- (7) Patients with peritonitis within 4 weeks of the first day of the screening period.
- (8) Patients with AST, ALT, or total bilirubin values of 2.5 times or greater the upper limit of standard during the screening period. This does not apply to patients with Gilbert's syndrome.
- (9) Patients with uncontrolled hypertension (defined as systolic BP >180 mmHg or diastolic BP >110 mmHg) during the screening period or on the first day of the treatment period.
- (10) Patients for whom any of the following apply upon funduscopy during the screening period:
  - ✓ No ocular fundus findings are possible.
  - ✓ Active ocular fundus disease.
- (11) Patients with severe cardiac failure from the day of consent (Class IV according to severity classification of the New York Heart Association (NYHA))
- (12) Patients with cerebrovascular disorders or acute coronary syndromes (hospitalization for unstable angina or myocardial infarction, etc.) within 12 weeks prior to the first day of the screening period. Patients who have been hospitalized due to acute coronary angioplasty or cardiac failure.

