- (13) Patients with malignant tumors or a history of such. However, this does not apply to patients with no relapse for 5 or more years (5 or more years with no relapse from last administration of chemotherapy if chemotherapy was used).
- (14) Patients with incidence or relapse of deep vein thrombosis or pulmonary embolism within 12 weeks prior to the first day of the screening period.
- (15) Patients with current or previous haemosiderosis or hemochromatosis.
- (16) Patients with a history of or plans for organ transplant (not including being on a waiting list for renal transplant), haematopoietic stem cell transplant, or bone marrow transplant.
- (17) Patients with an allergy to the study drugs.
- (18) Patients who have participated in another clinical study and received study drugs within 12 weeks prior to informed consent, or within 5 times the half-life of the study drug (whichever is longer).
- (19) Patients who have previously used MT-6548.
- (20) Patients with known low tolerance to HIF-PH inhibitors.

- (21) Patients who are unwilling to consent to use contraception from the beginning of the study period to 30 days following the final dose of the study drug for women who may become pregnant, or from the beginning of the study period to 90 days following the final dose of the study drug for men.
- (22) Female patients who are or may be pregnant, or women who are nursing.
- (23) Other patients judged by investigators/subinvestigators to be inappropriate as a subject in this study.

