## 12. Withdrawal criteria and procedures

### 12.1 Withdrawal criteria

Subjects will be withdrawn from the study if the following criteria are met:

- (1) If the subject expresses a desire to withdraw from the study.
- (2) If it is discovered that the subject is clearly ineligible for study participation.
- (3) If investigators/subinvestigators determine that AEs make continued participation in the study difficult.
- (4) If investigators/subinvestigators determine that continuation of the study is inappropriate for a subject, such as if hyperviscosity syndrome occurs or if control of Hb within the target range is impossible.
- (5) If continuous haemodialysis is initiated, or if the subject receives a renal transplant.
- (6) If renal function recovers such that peritoneal dialysis is discontinued.
- (7) If pregnancy of the subject is discovered.
- (8) If the investigator/subinvestigator determines a subject should withdraw from the study for any other reason.

Rationale

- (1) Set out of ethical considerations.
- (2) (5) (6) Set in order to prevent study drug administration to subjects unsuitable for inclusion in safety or efficacy evaluation.
- (3) (4) (7) Set out of safety considerations.
- (8) Set in order to allow the investigator/subinvestigator to make determinations regarding study continuation for significant safety-related reasons other than those enumerated above.

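### Inclusion criterion (4) requires subjects to be expected to start haemodialysis, which contradicts its own rationale and selects patients for a withdrawal criterion

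*Protocol*

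**What the plan says.** Section 3.2 of the Protocol opens with the rule "Subjects must meet all inclusion criteria below and have capacity to grant informed consent". Each numbered item is therefore a condition of entry.

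- Criterion (3) asks for at least 4 weeks of peritoneal dialysis before screening, "but excluding patients also receiving haemodialysis".
- Criterion (4) is "Patients expected to initiate haemodialysis during the treatment period". Section 3.2 of the Protocol Summary words it identically.
- The Rationale under section 3.2 explains (3) and (4) together: "Set because target patients are those receiving peritoneal dialysis with no concomitant haemodialysis".

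Later sections deal with subjects who leave peritoneal dialysis.

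- Withdrawal criterion (5), in Protocol Summary section 8 and Protocol section 12.1, is "If continuous haemodialysis is initiated, or if the subject receives a renal transplant". The rationale in section 12.1 for criteria (2), (5) and (6) is "Set in order to prevent study drug administration to subjects unsuitable for inclusion in safety or efficacy evaluation".
- Withdrawal criterion (6) covers recovery of renal function that ends peritoneal dialysis.
- Section 3.3 bars two such events at entry when they are foreseen. Exclusion (6) is "Patients expected to no longer require peritoneal dialysis during the study period due to recovery of renal function". Exclusion (16) begins "Patients with a history of or plans for organ transplant" and exempts patients who are only on a renal waiting list.

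**The concern.** Criterion (4) appears to have its direction reversed. It is stated as something a subject must satisfy, yet its stated purpose is to keep haemodialysis out of the study population.

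Eligibility criteria define to whom the results apply. With this wording, a reader cannot tell whether the trial studied patients expected to remain on peritoneal dialysis alone or patients expected to start haemodialysis. Protocol section 2 sets the objective as anaemia in PD-CKD. A cohort chosen because haemodialysis is imminent would be a poor basis for that objective, and some of its members would be withdrawn before the Week 20 and 24 haemoglobin assessments.

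Sites were not free simply to ignore the sentence. Section 8.2.3 keeps subjects found unsuitable out of the treatment period. Withdrawal criterion (2) removes subjects found to be clearly ineligible. Section 14.2 forbids deviation without prior written permission, except in a medical emergency.

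**Working it through.** The criterion carries no figure, so the check is a comparison of texts.

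**Step 1: is the wording a reading accident?** Criterion (4) is stated in two places, Protocol Summary 3.2 and Protocol 3.2. In 2 of 2 it is a complete sentence with no negation, no redaction mark and no gap. Text dropped when the PDF was read is an unlikely cause.

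**Step 2: set the criterion beside the related provisions.**

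| Provision | Where | What it does about haemodialysis |
|---|---|---|
| Inclusion (4) | Protocol Summary 3.2; Protocol 3.2 | Requires that its start be expected |
| Rationale for (3) and (4) | Protocol 3.2 | Target patients do not have it |
| Inclusion (3) | Protocol Summary 3.2; Protocol 3.2 | Bars patients already on it |
| Withdrawal (5) | Protocol Summary 8; Protocol 12.1 | Withdraws subjects who start it continuously |
| Rationale for withdrawal (5) | Protocol 12.1 | Such subjects are unsuitable for evaluation |

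The first two rows cannot both stand: requiring an expected start of haemodialysis does not serve a purpose of having none. Rows one and four are in tension, because the entry rule selects for an event that, if continuous, ends participation.

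**Step 3: compare the other ways out of peritoneal dialysis.** Withdrawal criteria (5) and (6) together name three: continuous haemodialysis, renal transplant and recovery of renal function.

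- Recovery, if expected: excluded at entry by exclusion (6). The Rationale in 3.3 lists (6) among the conditions likely to affect efficacy evaluation.
- Transplant, if planned: excluded at entry by exclusion (16), apart from waiting-list status.
- Haemodialysis, if expected: required at entry by inclusion (4).

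So 2 of 3 are exclusions when anticipated and 1 of 3 is an entry requirement.

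**Step 4: apply the literal rule to two patients.**

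- A stable peritoneal dialysis patient with no haemodialysis in prospect meets (3), fails (4) and does not enter.
- A peritoneal dialysis patient expected to start haemodialysis at, say, Week 16 meets (3) and (4). This patient enters, and is withdrawn under (5) if the haemodialysis is continuous.

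**Step 5: look for a correction elsewhere.** None of the readable exclusion criteria in 3.3 deals with expected haemodialysis. The SAP does not restate eligibility. The SAP Errata correct several items, but not this one.

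**Step 6: is any planned figure affected?** The only sample-size figure is the ±0.57 g/dL in Protocol section 6.1. It reproduces as t(0.975, 39) × 1.78/√40 = 0.569 and does not depend on criterion (4). The documents give no rate of haemodialysis initiation, so the effect of a literal reading on drop-out or precision cannot be sized.

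**The case against.** The strongest reply is that this is a slip in the English text alone. The shared rationale makes the intended direction plain to anyone reading section 3.2 as a whole, and if the original-language protocol is sound the trial was unaffected. That is plausible, but not established. The note saying the document was translated from Japanese belongs to the SAP Errata, not to the readable part of the Protocol. The Protocol Summary also gives the criterion with no rationale beside it.

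Four narrower points have some force.

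- Criterion (3) concerns status at entry and criterion (4) a later expectation, so one patient can satisfy both. The clash between them is one of intent, not of logic.
- Withdrawal (5) says continuous haemodialysis and criterion (4) does not, so the overlap is partial. The conflict with the rationale does not rest on that word.
- The grouping into three routes is a reading of withdrawal criteria (5) and (6), not a scheme the Protocol sets out, and exclusion (16) also covers past transplants. It supports the point but is not a measurement.
- Because (3) still applies, everyone enrolled would have PD-CKD at entry. The mismatch with the objective is that a literal reading selects an unrepresentative subset likely to leave peritoneal dialysis alone.

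Finally, enrolment was evidently complete when the SAP was finalised. Version 2 reflects the case review meeting, and the Errata report only two subjects in the Correction cohort. A correction cannot change who entered. It can still settle what the entry rule was.

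**Conclusion.** The concern holds. A mandatory eligibility criterion, as written, contradicts its own stated rationale, and it selects patients for an event that is a ground for withdrawal when continuous. The conflict between criterion (4) and its rationale would be enough alone; withdrawal criterion (5) and the handling of recovery and transplant support it.

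The contradiction rests on the visible text and needs no assumption. Three things remain open: the cause, whether sites worked from this wording, and whether enrolment was affected. No numerical effect is claimed. The text must be fixed, but a defect in the trial as conducted has not been shown.

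**What to change.** 1. Check criterion (4) against the original-language protocol.
2. Correct it in Protocol Summary 3.2 and Protocol 3.2 so that it agrees with its stated rationale, and reconcile it with criterion (3) and with withdrawal criterion (5) and its rationale (Protocol Summary 8, Protocol 12.1).
3. Issue the change as a formal correction that says whether the error was confined to the English text.
4. If sites used the wording as it stands, report how criterion (4) was applied at enrolment.

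The cost is a text correction in two places and one source check, plus the reporting in step 4 if it applies. No further patients or data collection are needed.
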